## CLINICAL TRIAL PROTOCOL SYNOPSIS

Name of company: Boehringer Ingelheim		Tabulated Trial Protocol	
Name of finished product: Not applicable			
Name of active ingredient: BI 1467335			
Protocol date: 09 March 2016	Trial number: 1386.8		Revision date: 05 OCT 2016
Title of trial: Safety, tolerability, pharmacokinetics and pharmacodynamics of multiple rising oral doses of BI 1467335 in healthy male and female subjects (double-blind, randomised, placebo-controlled within dose groups)			
Principal Investigator: [REDACTED]			
Trial site: [REDACTED]			
Clinical phase: I			
Objectives: To investigate safety, tolerability, pharmacokinetics and pharmacodynamics following multiple rising doses of BI 1467335			
Methodology: Double-blind, randomised, placebo-controlled within dose groups, parallel-group design			
No. of subjects:			
total entered: 36*			
each treatment: 12 per dose group (9 on active drug and 3 on placebo)			
* Additional subjects may be entered to allow testing of an additional dose within the approved dose range on the basis of experience gained during trial conduct (e.g. preliminary PK, ECG and safety data),. In this case up to 48 subjects may be included.			
Diagnosis: Not applicable			
Main criteria for inclusion: Healthy male/female of non-childbearing potential subjects, age of 18 to 50 years, body mass index (BMI) of 18.5 to 29.9 kg/m 			
Test product: BI 1467335, Powder for oral solution (PfOS)			
dose: Dose group 1: 10 mg BI 1467335, q.d. Dose group 2: 15 mg BI 1467335, q.d. Dose group 3: 20 mg BI 1467335, q.d.			
mode of admin.: Oral with 240 mL of water after an overnight fast of at least 10 h			
Comparator product: Solvent for Oral Solution (Sucralose 4 mg/ml + Menthol 2 mg/ml) as placebo			
dose: Not applicable			
mode of admin.: Oral with 240 mL of water after an overnight fast of at least 10 h			
Duration of treatment: 28 days with multiple doses of BI 1467335 q.d.			

Name of company: Boehringer Ingelheim		Tabulated Trial Protocol	
Name of finished product: Not applicable			
Name of active ingredient: BI 1467335			
Protocol date: 09 March 2016	Trial number: 1386.8		Revision date: 05 OCT 2016

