	23	528:00	08:00	Ambulatory visit, Drug administration 					x 		x 	
	24	552:00	08:00	Ambulatory visit, Drug administration 					x 		x 	
	25	576:00	08:00	Ambulatory visit, Drug administration 		x 			x 	x 	x 	
		577:00	09:00	Discharge		x			x	x	x	
	26	600:00	08:00	Ambulatory visit, Drug administration 		x 		▲	x 	x 	x 	
		601:00	09:00	Discharge		x			x	x	x	
	27	624:00	08:00	Ambulatory visit, Drug administration 		x 		▼	x 	x 	x 	
		625:00	09:00	Discharge		x			x	x	x	
		636:00	20:00	Admission to trial site		x 					x	

Visit	Day	Planned time (relative to first drug administration [h:min])	Approximate clock time of actual day [h:min]	Event and comment	Safety laboratory	PK blood 	PK urine 	PD blood 	12-lead ECG 	Vital signs (BP, PR)	Questioning for AEs and concomitant therapy 		
2	28	646:00	6:00		x 				x 	x 	x 		
		648:00	08:00	Last drug administration		x 	▼	x 					
		648:15	08:15			x 	▲						
		648:30	08:30			x 		x	x	x			
		648:45	08:45			x 		x	x	x			
		649:00	09:00			x 		x	x	x	x		
		649:30	09:30			x 		x	x				
		650:00	10:00	240 mL fluid intake and light breakfast 		x 		x	x	x	x		
		651:00	11:00			x 		x					
		652:00	12:00	240 mL fluid intake, thereafter lunch 		x 	+	x	x	x	x		
		654:00	14:00			x 		x					
		656:00	16:00	Snack (voluntary) 		x 	+	x	x	x	x		
		658:00	18:00	Dinner 		x 		x					
		660:00	20:00			x 	+	x	x	x	x		
		29		672:00	08:00	Ophthalmological investigation 		x 	▼	x	x	x	x
				673:00	09:00	Discharge from trial site (confirmation of fitness) 							
		30		696:00	08:00	Ambulatory visit	x	x		x	x	x	x
31		720:00	08:00	Ambulatory visit		x					x		
32		744:00	08:00	Ambulatory visit		x		x			x		
34		792:00	08:00	Ambulatory visit		x		x			x		
36		840:00	08:00	Ambulatory visit		x		x					
38		888:00	08:00	Ambulatory visit		x		x					
40		936:00	08:00	Ambulatory visit		x		x					

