3	42 to 48			End of trial (EOT) examination 	x			x	x	x	x		

1. Screening includes subject information, informed consent, physical examination, check of vital signs, ECG, safety laboratory (including drug screening), demographics (including determination of body height and weight, smoking status and alcohol history), relevant medical history, concomitant therapy and review of inclusion/exclusion criteria.
2. The time is approximate; the respective procedure is to be performed and completed within 2 h prior to drug administration. Allocation to treatment may be performed at any time following enrolment but must be completed prior to (first) drug administration.
3. If several actions are indicated at the same time point, the intake of meals will be the last action.
4. End of trial examination includes physical examination, body weight, vital signs, ECG, safety laboratory, recording of AEs and concomitant therapies. Confirmation of fitness includes physical examination.
5. Urine drug screening and alcohol breath test as well as pregnancy test in women will be done at this time point.
6. AEs and concomitant therapies will be recorded throughout the trial, but will be specifically asked for at the time points indicated in the [Flow Chart](#) above.
7. Safety laboratory, ECG, blood pressure assessment and AE questioning to be done and medically evaluated within 3 days prior to first administration of study drug; this visit can be omitted, if the screening examination is performed on Days -3, -2 or -1.
8. The ECG recording has to be performed as triple on Day 1 and Day 2, Day 14 and Day 15, Day 21, Day 28 and Day 29. All other ECG recordings will be single ECGs.
9. Sampling times and periods may be adapted based on information obtained during the trial (e.g. preliminary PK data) including addition of samples and visits as long as the total blood volume taken does not exceed 510 mL per subject.

[figure not shown]
---

Proprietary confidential information © 2016 Boehringer Ingelheim International GmbH or one or more of its affiliated companies

10. A blank urine sample (x) is to be obtained prior to the first administration of trial medication. Other urine samples are to be collected over the stated post-dose intervals ( ◀ — | — | — ▶ ) [on Day 1, Day 14 and Day 28 fractionated sampling 0-4, 4-8, 8-12, and 12-24 h, otherwise 0-24 hour collection].
11. Administration under fasting conditions, light breakfast (or snack) 2 h p.a.

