  - ALC below 3000/microliter (but greater 2500/microliter) if still present after 1 week
11. Thrombocytopenia will lead to individual discontinuation from trial medication if any of the following applies:
  - Thrombocytopenia, i.e. absolute platelet count (APC) below lower limit of normal at any time if associated with clinical signs or symptoms of bleeding
  - APC below 80,000/microliter at any time
  - APC below 100,000/microliter (but greater 80,000/microliter) if still present after 1 week

In addition to these criteria, the physician may discontinue subjects at any time based on his or her clinical judgment.

A subject can also be removed from the trial if eligibility criteria are being violated or if the subject fails to comply with the protocol (for instance, by non-adherence to dietary rules, or non-attendance at study assessments).

If a subject is removed from or withdraws from the trial prior to first administration of trial medication, the data of this subject will not be entered in the case report form (CRF) or trial database and will not be reported in the clinical trial report (CTR). If a subject is removed from or withdraws from the trial after first administration of trial medication, this will be documented and the reason for discontinuation must be recorded in the CRF. In this case, the data will be included in the CRF/trial database and will be reported in the CTR. At the time of discontinuation a complete end of trial examination will be performed if possible and the information will be recorded in the CRFs. If the discontinuation occurs before the end of the REP (see [Section 5.2.2.2](#)), the discontinued subject should if possible be questioned for AEs and concomitant therapies at or after the end of the REP in order to ascertain collection of AEs and concomitant therapies throughout the REP, if not contrary to any consent withdrawal of the subject. These discontinuations will be discussed in the CTR.

If it is known that a subject becomes pregnant during the trial, administration of the trial medication has to be stopped immediately, and the subject has to be removed from the trial. The subject is to be followed until she has given birth or until the end of pregnancy. The subject's data are to be collected until the end of the trial (last visit of last subject) and reported in the clinical trial report. For reporting of pregnancy and all related events refer to [Section 5.2.2.2](#).

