### **5.2.3 Assessment of safety laboratory parameters**

For the assessment of laboratory parameters, blood and urine samples will be collected by the trial site at the time points indicated in the [Flow Chart](#) after the subjects have fasted for at least 10 h. Overnight fasting is not required at the discretion of the investigator or designee for retests.

The parameters that will be determined are listed in [Tables 5.2.3: 1](#) and [5.2.3: 2](#). Reference ranges will be provided in the ISF, Section 10.

Manual differential white blood cell count or urine sediment examinations will only be performed if there is a clinically relevant abnormality in the automatic blood cell count or in the urinalysis, respectively.

Table 5.2.3: 1 Routine laboratory tests

Functional lab group	Test name
Haematology	Haematocrit
	Haemoglobin
	Red blood cell count (RBC)
	White blood cell count (WBC)
	Platelet count
Automatic WBC differential (relative and absolute)	Neutrophils, eosinophils, basophils, monocytes, lymphocytes
Manual differential WBC (if automatic differential WBC is clinically relevant abnormal)	Polymorphnuclear neutrophils (segs), band neutrophils (stabs), eosinophils, basophils, monocytes, lymphocytes
Coagulation	Activated partial thromboplastin time (aPTT)
	Prothrombin time (Quick's test and INR)
	Fibrinogen
Enzymes	Aspartate transaminase (AST/GOT)
	Alanine transaminase (ALT/GPT)
	Alkaline phosphatase (AP)
	Gamma-glutamyl transferase (GGT)
	Glutamate dehydrogenase (GLDH)
	Creatine kinase (CK)
	CK-MB, only if CK is elevated
	Lactate dehydrogenase (LDH)
	Lipase
	Amylase
Hormones 	Thyroid stimulating hormone (TSH)
	fT3, fT4
	FSH 
Substrates 	Plasma glucose
	Creatinine
	eGFR (derived from creatinine using CKD-EPI formula)
	Cystatine
	Total bilirubin
	Direct bilirubin
	Total protein
	Protein electrophoresis (only at screening examination)
	Albumin
	Alpha-1-Globulin
	Alpha-2-Globulin
	Beta-Globulin
	Gamma-Globulin
	C-Reactive Protein (CRP)
	Uric acid
	Total cholesterol
Triglycerides	
Electrolytes	Sodium
	Potassium
	Chloride
	Calcium
	Inorganic phosphate

Table 5.2.3: 1 Routine laboratory tests (cont).

Functional lab group	Test name
Urinalysis (Stix)	Urine nitrite Urine protein Urine glucose Urine ketone Urobilinogen Urine bilirubin Urine erythrocytes Urine leukocytes Urine pH

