Urine sediment (microscopic examination if erythrocytes, leukocytes nitrite or protein are clinically relevant abnormal in urine)	Only positive findings will be reported (for instance, the presence of sediment bacteria, casts in sediment, squamous epithelial cells, erythrocytes, leukocytes)

 Protein electrophoresis only at screening. Hormones only at screening and end of trial.

 Only if confirmation of postmenopausal stage is needed

The tests listed in [Table 5.2.3: 2](#) are exclusionary laboratory tests which may be repeated as required. The results will not be entered in the CRF/database and will not be reported in the CTR. Except for pregnancy test and drug screening, it is planned to perform these tests during screening only. Pregnancy testing in women will be performed at screening, Day -1, Day 13, Day 27, and as part of the end of trial examination. Drug screening will be performed at screening, Day -1, Day 13, Day 27 and end of treatment.

Table 5.2.3: 2 Exclusionary laboratory tests

Functional lab group	Test name
Drug screening (urine)	Amphetamine/MDA Barbiturates Benzodiazepine Cannabis Cocaine Methadone Methamphetamines/MDMA/XTC Opiates Phencyclidine Tricyclic antidepressants
Infectious serology (blood)	Hepatitis B surface antigen (qualitative) Hepatitis B core antibody (qualitative) Hepatitis C antibodies (qualitative) HIV 1+2-antibody/p24-antigen Combitec
Pregnancy test (urine)	Beta human chorionic gonadotropin (beta-HCG)

To encourage compliance with alcoholic restrictions, a breath alcohol test (Alcotest® 7410, Dräger AG, Lübeck, Germany) will be performed at screening and prior to each treatment period, and may be repeated at any time during the study at the discretion of an investigator or designee. The results will not be included in the CTR.

The laboratory tests listed in [Table 5.2.3: 1](#) and [5.2.3: 2](#) will be performed at [REDACTED] with the exception of the urinalysis (stix), drug screening and pregnancy tests. These tests will be performed at the trial site using, Combur 9 Test, MAHSAN® –Kombi/DOA10 rapid test and TestPack+Plus hCG Urin respectively.

Laboratory data will be transmitted electronically from the laboratory to the trial site.

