### 7.3.3 Safety analyses

Safety will be assessed for the primary endpoint and parameter of interest listed in [Section 5.2.1](#). All treated subjects (that is, all subjects who received at least one dose of study drug), will be included in the safety evaluation. Safety analyses will be descriptive in nature and will be based on BI standards.

Treatments will be compared in a descriptive way. The placebo control group in the safety evaluation will consist of all placebo treated subjects, regardless of the dose group in which they were treated. The active treatment groups will be compared to the placebo group in a descriptive way. Tabulations of frequencies/proportions will be used for the evaluation of categorical (qualitative) data, and tabulations of descriptive statistics will be used to analyse continuous (quantitative) data.

The analyses will be done by ‘treatment at onset’.

Measurements (such as ECG, vital signs, or laboratory parameters) or AEs will be assigned to treatments (see [Section 4.1](#)) based on the actual treatment at the planned time of the measurement or on the recorded time of AE onset (concept of treatment emergent AEs). Therefore, measurements planned or AEs recorded prior to first intake of trial medication will be assigned to ‘screening’, those between first trial medication intake until the trial termination date will be assigned to the treatment period, and those after the trial termination date will be assigned to ‘post-study’. These assignments including the corresponding time intervals will be defined in detail in the TSAP.

Adverse events will be coded using the Medical Dictionary for Regulatory Activities (MedDRA). Frequency, intensity according to CTCAE grading and causal relationship of AEs will be tabulated by treatment, primary system organ class and preferred term. SAEs, AESIs (see [Section 5.2.2.1](#)) and other significant AEs (according to ICH E3) will be listed separately.

Laboratory data will be compared to their reference ranges. Values outside the reference range will be flagged. Additionally, differences from baseline will be evaluated.

For vital signs, the differences from baseline will be evaluated.

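### Thyroid tests are scheduled only at screening and 14 to 20 days after the last dose, so completers have no thyroid reading during dosing

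*Protocol*

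**What the plan says.** Protocol Section 5.2.3 lists TSH, fT3 and fT4 in the hormone group of the routine laboratory table. FSH is in the same group but is measured only where postmenopausal status needs confirming. Footnote 1 to the table sets the timing for the group: "Hormones only at screening and end of trial".

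The synopsis gives the treatment duration as "28 days with multiple doses of BI 1467335 q.d". The Flow Chart places the row "Last drug administration" on Day 28 and the row "End of trial (EOT) examination" on Days 42 to 48. Flow Chart footnote 4 confirms that the visit includes laboratory work: "End of trial examination includes physical examination, body weight, vital signs, ECG, safety laboratory, recording of AEs and concomitant therapies".

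The Flow Chart also schedules safety laboratory tests during dosing, for example on Days 3, 7, 12, 14 and 28. Footnote 1 keeps the hormones out of all of them.

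Section 7.3.3 covers laboratory parameters in its period rule, under which "those between first trial medication intake until the trial termination date will be assigned to the treatment period". It also plans an evaluation of laboratory differences from baseline.

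**The concern.** The primary objective (Section 2.2) is safety and tolerability of 28 days of once-daily dosing. Thyroid function is listed as a routine safety test, yet the schedule cannot observe it while drug is being given. For a completer, the only post-baseline value is taken two to three weeks after dosing has ended. A change that appears on treatment and resolves in that time would leave no trace in the routine data.

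This is fixed by the protocol and cannot be left to the analysis plan. The plan can decide how values are grouped and labelled, but it cannot supply a reading that was never taken.

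There is a second, smaller consequence. Clinical laboratory results belong to the minimum data for the safety reviews in Section 3.1, and escalation requires data up to Day 28. No post-baseline thyroid value is scheduled for completers within those data.

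**Working it through.** **Inputs**
- Thyroid test times: screening and end of trial (Table 5.2.3: 1, footnote 1).
- Last dose: Day 28, planned time 648:00 (Flow Chart).
- End-of-trial window: Days 42 to 48 (Flow Chart, Visit 3).
- Pre-dose safety laboratory on Day 28: 646:00 (Flow Chart).
- Minimum interval from one dose group's last dose to the next group's first dose: 14 days (Section 3.1).
- Group size: 12 subjects, 9 active and 3 placebo (Table 3.1: 1).

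**Reproducing the Flow Chart's clock.** Planned time = (Day − 1) × 24 h.
- Day 28: 27 × 24 = 648 h, as stated.
- Day 40: 39 × 24 = 936 h, as stated.

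**Gap from last dose to the end-of-trial panel**
- Earliest: 42 − 28 = 14 days (14 × 24 = 336 h).
- Latest: 48 − 28 = 20 days (20 × 24 = 480 h).

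**Scheduled thyroid panels for a completer**

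| Period | As planned | With a Day 28 panel added |
|---|---|---|
| Before dosing (screening) | 1 | 1 |
| During dosing (Days 1 to 28) | 0 | 1 |
| After dosing (Days 42 to 48) | 1 | 1 |

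The Day 28 sample at 646:00 is taken 648 − 646 = 2 h before the last dose. It is 646 − 624 = 22 h after the Day 27 dose, so 27 doses have been given by then.

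**Timing against escalation.** The next group may start as early as Day 28 + 14 = Day 42 of the previous group's last cohort. That is the day on which the end-of-trial window opens. A Day 28 value would fall within the data required for escalation, whereas an end-of-trial value need not.

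**Reach of a change now.** The rationale for global amendment 3 (Section 11) says that the 10 mg group has completed its treatment period. That leaves 36 − 12 = 24 planned subjects at 15 and 20 mg, of whom 2 × 9 = 18 are on active drug and 2 × 3 = 6 on placebo. The pooled placebo group would have 9 subjects, 6 of them with a scheduled Day 28 thyroid value.

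**The case against.** The strongest reply is that nothing here is contradictory. Footnote, Flow Chart and Section 7.3.3 agree with one another, and testing at entry and exit is a legitimate choice for a routine panel. The available text names no thyroid signal, no thyroid event of special interest and no thyroid stopping rule. The primary endpoint is subjects with drug-related adverse events. Subjects are questioned for adverse events throughout dosing, and unscheduled tests remain possible. All of this stands, and it limits the impact. It does not remove the gap.

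A reader might infer three stronger points that the documents do not support.

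- **That the end-of-trial value is wrongly labelled as on treatment.** The broad treatment period is deliberate. Section 5.2.2.2 gives the reason for the matching adverse-event rule: the residual effect period is not yet known. Section 7.3.3 leaves the detailed intervals to the statistical analysis plan, which is not shown. Nothing says that end-of-trial values will be pooled with visits during dosing.
- **That most of any effect would have gone by Day 42.** The documents give no reversal half-life, so the share remaining cannot be calculated. The rationale for amendment 3 says that steady state was not reached after four weeks at 10 mg, and PK sampling runs to Day 40. The end-of-trial value is post-dosing, but it is not shown to be drug-free.
- **That the table mixes two kinds of value.** For subjects who stop early, Section 3.3.4.1 says: "At the time of discontinuation a complete end of trial examination will be performed if possible". Their value could be close to dosing. This needs early stoppers, however, and the amendment rationale reports that every 10 mg subject completed treatment.

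The cost objection stands in part. The text does not say whether the existing Day 28 tube has volume for three more assays, and total blood per subject is limited to 510 mL. The stability samples in Section 5.5.2.4 already use 3 × 3.6 = 10.8 mL per subject at 10 and 15 mg.

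**Conclusion.** The point holds as a scheduling gap of modest impact. Completers have no scheduled TSH, fT3 or fT4 reading during dosing, and their single post-baseline reading comes 14 to 20 days after the last dose. A thyroid change that reverses within that time would be missed, and the trial as planned cannot support a statement about thyroid function on treatment in completers.

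The gap follows from the protocol's own dates and needs no assumption. Its clinical importance is open: the residual effect period is unknown, so a persisting effect might still be seen at end of trial, and no thyroid concern appears in the available text. It does not bear directly on the primary endpoint. It is worth correcting because the correction is small and uses a sample already scheduled.

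**What to change.** For the dose groups still to be treated, change footnote 1 so that TSH, fT3 and fT4 are measured at screening, on the Day 28 pre-dose safety laboratory sample (646:00), and at end of trial. FSH stays under footnote 2.

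Keep the end-of-trial panel. While the residual effect period is unknown, a late reading has value of its own, and moving the panel to Day 28 would replace one gap with another.

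In the analysis, show thyroid values by visit, with Day 28 as the value during dosing and completers' end-of-trial values as post-dosing. This can be done within the interval definitions that Section 7.3.3 leaves to the analysis plan, without changing the general treatment-period rule.

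**Cost:** one extra assay panel per subject, 24 in all for the planned 15 and 20 mg groups, with no new visit. Any added blood must be checked against the 510 mL limit. The 10 mg group, including its 3 placebo subjects, will lack the Day 28 value, so that comparison rests on 6 of the 9 planned placebo subjects and the report should say so.

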## 5.2.4 Electrocardiogram

### 5.2.4.1 12-lead resting ECG

Twelve-lead resting ECGs (I, II, III, aVR, aVL, aVF, V1 - V6) will be recorded using a computerised electrocardiograph (CardioSoft EKG System, GE Medical Systems, Freiburg, Germany) at the time points given in the [Flow Chart](#). Electrode placement will be performed according to the method of Wilson, and modified Goldberger and Einthoven (Mason-Likar). The same electrode positions on a specific subject should be used for all ECG recordings throughout the study.

Triple ECGs (recorded within 180 sec) will be recorded on all time points on Day 1, Day 2, Day 14, Day 15, Day 21, Day 28 and Day 29. On all other visits/time points single ECGs will be obtained. ECGs may be repeated for quality reasons (like alternating current artefacts, muscle movements, electrode dislocation). For time points with triple ECGs, all three single ECGs will be repeated.

In order to achieve a stable heart rate at rest and to assure high quality recordings at comparable resting phases, all ECGs will be recorded for 10-sec duration after the subjects have rested for at least 5 min in a supine position. The site personnel will be instructed to assure a relaxed and quiet environment so that all subjects are at complete rest during the recordings. ECG assessment will always precede all other study procedures of the same time point (except blood drawing from an intravenous cannula which is already in place) to avoid impact of sampling on the ECG quality.

All locally printed ECGs will be evaluated by the investigator or a designee. Additional (unscheduled) ECGs may be collected by the investigator for safety reasons. These ECGs are assigned to the prior scheduled time point. Unscheduled ECGs will not be included into the statistical analysis of interval lengths.

For the inclusion or exclusion (see [Section 3.3](#)) of a subject and for the assessment of cardiac safety during the study, the QT and QTcB values generated by the ECG machines or their manual corrections by the investigators will be used. In doubtful cases, ECGs may be sent upfront for centralized evaluation (see below). In this case, these centrally measured results would overrule any other results obtained.

Abnormal findings will be reported as AEs (during the trial) or baseline conditions (at screening) if judged clinically relevant by the investigator. Any ECG abnormalities will be monitored carefully and, if necessary, the subject will be removed from the trial and will receive the appropriate medical treatment.

All recorded ECGs will be sent electronically to an independent ECG core lab. The centralised evaluation of all 12-lead ECGs recorded on Day 1 to Day 4, Day 7, Day 14 to

Day 17, Day 21, and Day 28 to Day 29 will be performed by an independent ECG laboratory. In case it is needed ECGs recorded at other visits/time points may also undergo centralized evaluation.

For this analysis, all cardiac intervals (PR, QRS, RR and and QT intervals) will be determined semi-automatically, whereas PR and QRS intervals are determined by a validated GE 12-SL-algorithm or equivalent. Other parameters (e.g. cardiac axis) are determined by a validated GE 12-SL-algorithm or equivalent but do not undergo semiautomatic evaluation. All interval measurements for each subject will be performed on the same lead. The intervals will be measured from four cardiac cycles (beats) in lead II. If lead II shows a flat T wave or is not measurable for any reason, lead V5 will be used, or if that lead is not measurable, then lead I will be used. The lead actually used will be reported in the CTR.

For blinding status see [Section 4.1.5.1](#). No more than two different blinded readers will evaluate all ECGs of the study. For quality assurance and control of the measurements, all ECGs of a subject will be subsequently reviewed by the ECG technician supervisor or his/her designee with respect to the overall variance of the measured intervals, in order to detect accidentally switching of leads and/or false subject assignments of the ECGs. After the quality control the fiducial point markings will be reviewed by the cardiologist assigned to the study. Abnormalities detected during centralized ECG evaluation will not necessarily qualify as AE.

The results of the centralized evaluation will be sent from the ECG core lab to the data management of BI according to a pre-specified data transmission agreement.

Assessed ECGs will comply with the ICH E14 guidance document and supplements [[R05-2311](#), [R13-0801](#), [R13-4095](#)] as well as the FDA requirements for annotated digital ECGs [[R09-4830](#)].

